Patients at high risk of emergency hospital admission (top quintile) or with long-term conditions are offered enrolment in the programme during the course of a consultation with their General Practitioner (GP). Enrolment on the programme is considered complete if patients consent to be enrolled on the programme and consent for their data to be shared with the WELC Integrated Care Programme partners, and this consent is recorded on the electronic patient record by the GP. Enrolment started in April 2012, with a total of 29 patients enrolling in the first 12 months. The following fiscal year (2013-2014) saw another 906 patients enrol on to the programme. Numbers are increasing rapidly, with currently 11,940 patients on the pathway (1.3% of all patients, in comparison to the 20% targeted) (source: WELC Data Cube).

The integrated care programme is trying to achieve its goals through a combination of patient engagement; joint decision making and accountability; clinical leadership and culture development; information sharing and decision support; and aligned incentives and reimbursement models. Although patients are either enrolled or not enrolled on the programme, the actual intervention may differ from patient to patient and across different CCGs. The Integrated Care Programme comprises nine categories of interventions:

1. Self-care, behaviour and expectation management;
2. Care planning;
3. Health and social care navigation;
4. Case management;
5. Specialist input in the community;
6. Discharge support for mental health patients from secondary to primary care;
7. Rapid response with short term re-ablement;
8. Mental health liaison; and
9. Discharge support from the acute community.

The exact interventions can be specific to local arrangements, and so are difficult to generalise across a larger population. Therefore, the evaluation proposed in this protocol aims to evaluate the overall effect of enrolment onto the integrated care pathway, rather than looking at effect of the individual

interventions offered during this pathway. We will, however, try to describe the occurrence of particular interventions.

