A small number of patients provided consent to be on the pathway or for their data to be shared but not both. Because there is some ambiguity about the care received by these patients, they will be excluded from the study.

The initial findings of the evaluation will be based on outcomes over the six months following enrolment. This relatively short follow-up period will allow for timely results by the end of 2015. Further analysis will be based on a follow-up period of twelve months following enrolment; however patient-level data required for this analysis are not expected to be available before February 2015 (see ‘Timescale’ below for more details).

Intervention

The focus of this study is to evaluate the overall integrated care pathway, and thus we will assess patient outcomes from the date of enrolment onto this pathway. After the enrolment on the programme a patient will receive specific interventions at varying intervals that greatly influence the effect of the overall ‘treatment’ (see figure below).

We will report the overall duration of time spent on the integrated care pathway using Kaplan-Meier curves (Kaplan & Meier 1958). These show the proportion of patients remaining on the pathway after various numbers of days spent on the pathway. In some cases, the lag between enrolment on the pathway and receiving first ‘different-from-normal’ care might be substantial, and so we will explore whether the individual interventions illustrated in the figure below can be identified from the line-level data.

Endpoints

The Integrated Care Program has identified a wide range of Key Performance Indicators (KPIs). These indicators span: quantitative metrics to assess how care is being integrated; metrics on reviews of individual patient cases and care plans; and metrics of health care utilisation. This last category of indicators is most relevant to this study and includes:

- Number of GP appointments (*e.g.*, per head, per 12 months);
- Number of urgent referrals;
- Number of hospital bed days per patient;
- Number of weekend discharges from hospital;
- Secondary care cost (PbR);
- Number of emergency hospital admissions;
- Number of avoidable hospital admissions;
- Number of A&E attendances; and
- 30-day hospital readmission rates.

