Our primary endpoint is the number of emergency hospital admissions per patient, which is a commonly used endpoint in evaluative studies of integrated care. Our secondary endpoint is the number of hospital bed days per patient over twelve months, as this reflects changes to the length of stay in hospital as well as the number of admissions.

Other endpoints will be the notional cost of care per patient, including primary and secondary care cost and other indicators listed above.

Sample size calculation

Our sample size will be sufficient to identify a 15% change in emergency admissions between the enrolled patients and the matched control group. Our sample size calculation was performed in SAS with 90% power and a two-sided p-value of 0.05. We assumed an average number of emergency admissions per patient per year of 0.6 with a standard deviation of 1.4. These assumptions are based on a previous study with a similar population base (Steventon, Bardsley, Billings, Dixon, et al. 2012).

The sample size calculation indicate that in order to identify a 15% change in emergency admission a sample size of 10,174 is required in case of a balanced sample (1 control per enrolled patient), or 11,445 in case of a sample with two controls per enrolled patient. In comparison, we estimate that our study will include at least 6,360 integrated care patients. In a matched control design with one control patient per integrated care patient, the total sample size would therefore be 12,720 patients. If there were two control patients per integrated care patient, the total sample size would be higher, at 19,080.

Control group

In the absence of a randomised controlled trial, we will compare the outcomes of the integrated care cohort with a retrospectively matched control group. In other words, line-level routine, patient information will be used to characterise the integrated care patients as well as possible, and then select, for every patient, matched controls that were not enrolled onto the programme but had similar observed characteristics to the enrolled patient. These matched patients will form the control group for the evaluation of the programme.

Control patients will be registered with a general practice in the WELC area, and will not have been enrolled onto the integrated care pathway at any point before the end of our follow-up period.

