Preliminary analysis of aggregated data from the WELC Integrated Care Programme (using the Data Cube) suggests that the pool of potential matches is sufficiently large to select matched controls within cluster (*i.e.*, geographically clustered GPs) and within the same risk-band (top 0.5%, 0.5-5%, or 5-20%). This is because enrolment rates at cluster level vary between 17% and 38%, and enrolment rates for the different risk-bands are 50%, 24% and 2%, respectively.

Matching will be done to optimise the similarity of integrated care and matched control groups with respect to variables that are likely to be predictive of the endpoints. These variables will include:

predictive risk score; age; gender; ethnicity; prior primary and secondary care utilisation; a measure of socioeconomic deprivation (the Index of Multiple Deprivation, attributed to the Lower Super Output Area of residence); existing diagnoses of health care conditions; and numbers of prescription medications. Many of these variables feature in the Combined Predictive Model (Wennberg et al. 2006), but are included in our matching algorithm so that the groups will be similar in terms of these more detailed variables as well as the overall risk score.

To increase the number of potential controls available for the analysis, we will assign each potential control up to 12 index dates, one for each month from January 2014 to December 2014, assuming that the patient is alive at each of these time points. Baseline variables (*e.g.*, age and prior primary and secondary care utilisation) will then be calculated at each of these index dates, and each control patient will provide the matching algorithm with up to twelve observations.

Matched control observations will be selected using the genetic matching algorithm, which is a computer-intensive search procedure that produces more closely balanced groups than traditional approaches such as nearest neighbour matching on the propensity score (Sekhon & Grieve 2012). Balance will be assessed using the standardised difference, which is defined as the difference in means as a proportion of the pooled standard deviation (Austin 2009). Although the standardised difference would ideally be minimised without limit, a threshold of 10% has been used to describe meaningful difference (Normand et al. 2001). We will adjust the parameters in the genetic matching algorithm until we obtain standardised differences below these thresholds.

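### Where consent is recorded at the enrolment consultation, that visit counts as follow-up for enrolled patients only and inflates GP appointments and primary-care cost

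*Protocol*

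**What the plan says.** **Enrolled patients.** The protocol's Introduction says that eligible patients "are offered enrolment in the programme during the course of a consultation with their General Practitioner (GP". Enrolment is complete when the patient has consented both to joining and to data sharing, and "this consent is recorded on the electronic patient record by the GP". Methods, Intervention, sets the time origin: "we will assess patient outcomes from the date of enrolment onto this pathway".

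**Controls.** Methods, Control group, says "we will assign each potential control up to 12 index dates, one for each month from January 2014 to December 2014". The only condition placed on a date is in the same sentence: "assuming that the patient is alive at each of these time points". Controls must also be registered with a practice in the area and stay unenrolled to the end of follow-up, but no GP contact is required on or near the index date. On matching variables, the section adds: "Baseline variables (*e.g.*, age and prior primary and secondary care utilisation) will then be calculated at each of these index dates".

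**Endpoints.** The indicators listed under Methods, Endpoints, include "Number of GP appointments (*e.g.*, per head, per 12 months". The same section says: "Other endpoints will be the notional cost of care per patient, including primary and secondary care cost and other indicators listed above". Emergency admissions are the primary endpoint and bed days the secondary one. Methods, Study cohort, plans initial findings at six months and a further analysis at twelve.

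**The concern.** The two groups have different kinds of day 0. For an enrolled patient it is normally a day with a GP consultation, because that is where enrolment happens. For a control it is a calendar date, with a consultation only by chance. If outcomes are counted from day 0 inclusive, one GP contact enters follow-up in one group and almost none in the other.

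Matching cannot correct this, because it acts on use before the index date. Regression on baseline variables cannot either. The offset stays even with perfect baseline balance, because it comes from the counting window.

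Putting the day-0 contact into the baseline instead would not help. It would raise prior primary-care use in enrolled patients only, and matching would then look for controls who are heavier GP users.

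At stake is whether a programme with no effect would be reported as raising GP use and primary-care cost. The Executive summary names the cost of primary and secondary care as one of three focuses, and the Handover section foresees reuse of the code monthly or quarterly, so the convention would be carried forward.

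**Working it through.** **The plan's own figure.** The protocol gives no figure for GP contacts. Its only calculation is the sample size for emergency admissions: mean 0.6, SD 1.4, a 15% change (0.15 × 0.6 = 0.09), two-sided 0.05, 90% power. Per group, n = 2 × (1.960 + 1.282)² × 1.4² / 0.09², which gives 5,086, or 10,172 in total, against 10,174 stated. With two controls per enrolled patient the total is 11,442, against 11,445 stated. These figures reproduce, and the present point does not depend on them.

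**Inputs for the check.**
- Time origin, enrolled: date of enrolment (Methods, Intervention).
- Time origin, controls: monthly index date, alive (Methods, Control group).
- Windows: six and twelve months (Methods, Study cohort).
- Enrolled patients: at least 6,360 (Sample size calculation).
- Usual GP contacts per year, m: not in the documents; assumed 4 to 20.
- SD of GP contacts: not in the documents; assumed 5 to 15.

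**Formula.** Suppose there is no programme effect and the consultation falls on day 0. Over T months a control expects μ = m × T/12 contacts. An enrolled patient expects one contact on day 0 plus the usual rate on the remaining days: 1 + μ - m/365. The difference is 1 - m/365, and the relative excess is (1 - m/365)/μ.

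| m per year (assumed) | Excess contacts | Excess over 12 months | Excess over 6 months |
|---|---|---|---|
| 4 | 0.989 | 24.7% | 49.5% |
| 6 | 0.984 | 16.4% | 32.8% |
| 10 | 0.973 | 9.7% | 19.5% |
| 15 | 0.959 | 6.4% | 12.8% |
| 20 | 0.945 | 4.7% | 9.5% |

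The absolute excess hardly changes with m. The percentage doubles at six months because a fixed count is set against half the follow-up.

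**If only some consents are recorded on the consultation day.** With a share f of enrolled patients affected, the excess is f × (1 - m/365). For example, f = 0.5 and m = 10 give 0.5 × 0.973 / 10 = 4.9% over twelve months.

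**Would it be visible?** With 6,360 per group, and ignoring matching and reuse of controls, the standard error of a difference in means is SD × √(2/6,360). This is 0.09, 0.18 or 0.27 for an assumed SD of 5, 10 or 15. An excess of 0.97 is then about 11, 5.5 or 3.6 standard errors. Under these assumptions a null effect would probably be declared a significant increase.

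**Cost.** The offset is the unit cost of one GP contact × (1 - m/365). As a share of total cost it needs that unit cost and the mean total cost per patient. The documents give neither, so no percentage follows.

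**The case against.** Four objections carry weight.

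1. *Day 0 is not clearly inside the window.* The sentence in Methods, Intervention, mainly chooses enrolment as the origin rather than the first changed care. Methods, Study cohort, describes both periods as following enrolment, which can be read as starting after it. Whether day 0 is included is often left to an analysis plan, and none is shown. It stands that two readings exist. But the protocol does state an origin for each group, and the two origins are not comparable. The point concerns what is stated, and the two readings give materially different results for GP contacts.

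2. *Not every patient is affected.* A reader might infer that each enrolled patient gains a contact by construction. The documents do not support that. They place the offer in a consultation, but do not say that the offer, both consents and the recording share one date. If recording comes later, the contact precedes day 0. This stands, so the figures are upper limits.

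3. *The visit may be real programme use.* The aim is the overall effect of enrolment. If the consultation was arranged for enrolment, leaving it out would understate programme input. This stands as a possibility. The protocol does not say that the visit is counted on purpose, and reporting it separately serves both views.

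4. *Excluding day 0 for all outcomes would do harm.* A same-day admission or urgent referral arising from the enrolment consultation would be removed mainly from the enrolled group. This stands and limits the remedy to GP appointments and primary-care cost.

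**Conclusion.** The point holds in limited form. Read as written, the plan puts the enrolment consultation into follow-up for those enrolled patients whose consent is recorded that day, and gives controls no counterpart. The excess is up to about 0.95 to 0.99 GP contacts per enrolled patient, or about 5-25% over twelve months and 10-50% over six, for an assumed 4 to 20 contacts a year. The direction is certain where the mechanism operates: enrolled patients look like heavier GP users. The percentages rest on an assumed rate and on same-day recording.

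The affected endpoints are GP appointments and the primary-care part of cost, both in the protocol's third tier. A reader might infer that total cost is distorted to a similar degree; the documents contain nothing from which that could be worked out. Nor do they support extending the point to emergency admissions or bed days, because a GP consultation is neither. The change is worth making because it is nearly free, but it does not threaten the primary result.

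**What to change.** Add to the protocol, for GP appointments and primary-care cost only:

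- Start counting the day after the enrolment date (enrolled) or the index date (controls).
- End the window for prior primary-care use the day before that date in both groups, so that day 0 lies in neither window.
- Report the enrolment consultation separately as a programme input, with a sensitivity analysis that counts it.
- Leave the counting window for the hospital endpoints unchanged.

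This costs a short paragraph and a one-day shift in the derivation code for two endpoints and one set of matching variables. The sample size does not change. The small downside is that genuine day-0 primary-care contacts drop out of the main count.

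The change removes only the fixed day-0 excess. Enrolled patients would still be selected at a moment of GP contact and controls would not, and that difference should be acknowledged when the GP-use results are interpreted.

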The matching will be conducted with replacement, meaning that a patient might be used as the control for multiple integrated care patients. Our preference is to select two control observations per patient, as this would increase the precision of our estimates of the effect of the integrated care pathway on patient outcomes (*i.e.*, reduce the width of our confidence intervals, meaning we can be more sure about the effect size). However, if it is not possible to obtain adequate balance when selecting two controls per patient, we will rerun the matching algorithm when selecting one control per patient.

Statistical method

After adequate balance has been obtained, we will estimate the effect of the integrated care pathway on patient outcomes by fitting regression models to the data. These models will adjust for residual differences remaining between the groups in the baseline variables after matching. We will include all patients in these analyses, even if they died or moved away from the WELC area during the 12-month follow-up period.

For our primary endpoint, number of emergency hospital admissions, use of Poisson regression seems appropriate, but depending on the empirical distribution of this endpoint, alternative distributions will be considered (*e.g.*, negative binomial). We assume that ordinary least squares (linear) regression will be used

for our secondary endpoint, the number of hospital bed days. On receipt of the line-level data, we will test the suitability of these assumptions, and consider alternative distributions if appropriate. We will follow a similar procedure for other endpoints making sure that assumptions on distributions are appropriate.

Subgroup analysis

The main analysis will be pooled across all three CCGs and across all risk bands, as this approach is necessary to ensure adequate sample size. However, we will also examine whether there is evidence that the integrated care pathway affected the outcomes of certain subgroups of patients more or less than average. Specifically, we will examine subgroups defined by CCG (Newham, Tower Hamlets, and Waltham Forest) and risk band (top 0.5%, 0.5-5%, and 5-20%). We will also distinguish between patients with and without a recorded mental health condition.

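### The sample size assumes independent patients and the effect models name no variance for practice clustering or reused controls, so the intervals may be too narrow and the sufficiency claim is conditional

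*Protocol*

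**What the plan says.** Protocol, Sample size calculation, opens with a firm claim: "Our sample size will be sufficient to identify a 15% change in emergency admissions between the enrolled patients and the matched control group". The method is given only in outline: "Our sample size calculation was performed in SAS with 90% power and a two-sided p-value of 0.05". The outcome inputs are a mean and an SD, taken from a cited study: "We assumed an average number of emergency admissions per patient per year of 0.6 with a standard deviation of 1.4". The required totals are 10,174 for one control per enrolled patient and 11,445 for two. The expected totals are 12,720 and 19,080, built on at least 6,360 enrolled patients. No ICC, design effect or other variance inflation appears.

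Protocol, Statistical method: "we will estimate the effect of the integrated care pathway on patient outcomes by fitting regression models to the data". The models adjust for residual baseline differences. Poisson regression (or an alternative such as negative binomial) is named for emergency admissions and ordinary least squares for bed days. There is no practice term, random effect or clustered variance.

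Four other statements bear on independence:

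- Introduction: eligible patients "are offered enrolment in the programme during the course of a consultation with their General Practitioner (GP"), and the GP records the consent.
- Introduction: "The exact interventions can be specific to local arrangements".
- Control group: "enrolment rates at cluster level vary between 17% and 38" per cent, where a cluster is a geographic group of GPs. The control pool is judged large enough to match within cluster and risk band, but neither cluster nor practice is in the list of matching variables that follows.
- Control group: each potential control supplies up to 12 monthly observations, and matching is with replacement, preferably two controls per patient.

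**The concern.** Outcomes of patients in one practice tend to be correlated, because they share GPs, referral habits and local services. If enrolment also differs between practices, part of the contrast between enrolled and control patients is a contrast between practices, and a patient-level standard error understates its uncertainty. Matching within a geographic group of GPs removes differences between groups, but not those between practices inside a group. A control used several times, or present under several index dates, adds less information than the same number of distinct people.

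Two things are at stake. The first is the width of the interval on the primary effect, on which operational decisions about the programme would rest. The second is the unqualified statement that the sample will be sufficient.

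**Working it through.** **Reproducing the plan.** Difference sought: 0.15 × 0.6 = 0.09 admissions per patient per year; SD 1.4.

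- Normal approximation, 1:1: n per group = 2 × (1.960 + 1.282)² × 1.4² / 0.09² ≈ 5,085.1, rounded up to 5,086, so 10,172 in total.
- Normal approximation, 1:2: 11,442 in total.
- With the noncentral t distribution the totals are 10,174 and 11,445, exactly as stated.

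The stated totals therefore contain no allowance for dependence.

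**Power at the planned numbers, independent patients.**

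- 1:1: SE = 1.4 × √(1/6,360 + 1/6,360) = 0.0248. Power = Φ(0.09/0.0248 − 1.96) = 95.2%.
- 1:2: SE = 1.4 × √(1/6,360 + 1/12,720) = 0.0215. Power = 98.7%.

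**Margin before power falls below 90%.** 12,720/10,174 = 1.25 (1:1); 19,080/11,445 = 1.67 (1:2).

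**Practice clustering.** Patients are enrolled individually, so both groups can occur in one practice. The relevant form is then DEFF = 1 + (m − 1) × ρ_enrol × ρ_outcome. Here m is the planned total divided by the number of practices, ρ_outcome is the outcome ICC, and ρ_enrol is the practice-level correlation of enrolment that remains after matching. None of these is in the documents, apart from the planned totals. Assumed: 70 to 115 practices (the protocol's 11,940 patients at 1.3% imply about 918,000 people), ρ_outcome 0.005 to 0.02, ρ_enrol 0.05 to 0.30. Power uses SE × √DEFF. If the dependence is ignored, coverage of a nominal 95% interval is 2Φ(1.96/√DEFF) − 1.

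| Practices, ρ_outcome, ρ_enrol | Ratio | m | DEFF | Power | Coverage |
|---|---|---|---|---|---|
| 115, 0.005, 0.05 | 1:1 | 110.6 | 1.03 | 95% | 94.7% |
| | 1:2 | 165.9 | 1.04 | 98% | 94.5% |
| 90, 0.01, 0.20 | 1:1 | 141.3 | 1.28 | 89% | 91.7% |
| | 1:2 | 212.0 | 1.42 | 94% | 90.0% |
| 70, 0.02, 0.30 | 1:1 | 181.7 | 2.08 | 71% | 82.5% |
| | 1:2 | 272.6 | 2.63 | 73% | 77.3% |

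Example, middle row, 1:1: 1 + 140.3 × 0.20 × 0.01 = 1.28.

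**Control reuse.** Suppose each control is used r times on average, equally, and repeated uses carry no new information (both assumed). Then SE = 1.4 × √(1/6,360 + r/6,360) for 1:1 and 1.4 × √(1/6,360 + r/12,720) for 1:2. Power (1:1 / 1:2) is 90.0% / 97.2% at r = 1.5, 84.1% / 95.2% at r = 2 and 72.7% / 90.0% at r = 3. Controls at different index dates share only part of their follow-up, which would soften this; unequal reuse would worsen it.

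**The case against.** The strongest reply is that the dependence may cost little.

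- **The numbers have room.** The 90% is the power at the required total; the planned totals give 95.2% or 98.7% under independence. In the mid-range case the preferred two-control design keeps 94%. This stands.
- **The enrolment correlation is assumed.** The only place-level figure is the 17% to 38% range across clusters, which converts to about 0.02 to 0.055. At 0.055, with 70 practices and outcome ICC 0.02, the design effect is 1 + 180.7 × 0.055 × 0.02 = 1.20 (1:1) or 1 + 271.6 × 0.055 × 0.02 = 1.30 (1:2), and power is 91% or 96%. This stands too, with one reservation: the range describes groups of GPs, and practices inside a group may differ more.
- **Matching and adjustment may shrink the problem.** If controls are matched exactly within the correlated unit and the effect is common to all units, the variance factor is about 1 − ICC, and intervals that ignore clustering are slightly too wide. Adjustment for risk score, prior use and deprivation may also lower the outcome ICC. But the protocol presents within-cluster matching as feasible, not as a fixed rule, and a cluster is not a practice.
- **A statistical analysis plan may settle the variance.** That is possible, and the model text alone would be weak evidence. The sample size calculation and its sufficiency claim, however, are fixed in this protocol.

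A reader might infer that enrolled patients come mainly from high-enrolling practices and controls from low-enrolling ones. The protocol gives no practice-level enrolment rates, so this is conjecture. Nor does the full design effect 1 + (m − 1) × ICC for treatment assigned by whole practices apply, because consent is individual.

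**Conclusion.** The point holds in conditional form. The required totals rest on independent patients, while the protocol itself describes enrolment through GPs, locally arranged care and repeated use of controls, and names no variance that reflects them. The 95% intervals may be too narrow, and sufficiency depends on a design effect no larger than 1.25 (1:1) or 1.67 (1:2), from practice clustering and control reuse together.

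Under the assumed ranges the clustering design effect is 1.03 to 2.08 (1:1) or 1.04 to 2.63 (1:2): negligible at one end, serious at the other. These ranges are assumptions, not figures from the documents. The margins also take the protocol's 6,360 enrolled patients at face value.

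The stronger reading, that the study fails to reach 90% power or that its intervals are certainly too narrow, is not supported. Without an ICC, a practice count or a reuse rate, the documents cannot establish either.

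**What to change.** **Statistical method.** Use cluster-robust variance at GP practice for all effect models. Keep every observation of a reused control in one cluster, for example by assigning practice at the first index date; otherwise a control who changes practice could fall into two. A practice random intercept alone is not enough, because repeated records of the same person stay correlated beyond what their practice explains.

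**Sample size calculation.** State that 10,174 and 11,445 assume independent patients. Apply a stated design effect for practice clustering and control reuse, with the ICC estimated from the pre-2014 part of the data already requested (the extract starts on 1 January 2011). Restate the power or the detectable change for both 1:1 and 1:2. If the margin is exceeded, report the larger detectable change; no additional patients need be enrolled.

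**Cost.** Protocol wording, one variance option in the model code and one estimate from baseline data. The price is somewhat wider intervals and a less favourable power figure.
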